7.5.3. Time-to-Event Endpoints

For the following time-to-event endpoints, daily WI-NRS scores during the DBVC period will be used for the analysis:

- Time to \geq 2-point improvement from baseline in WI-NRS score
- Time to \geq 4-point improvement from baseline in WI-NRS score

A log-rank test stratified by randomization stratification factors will be used for between—treatment group comparisons. The hazard ratio and 95% CI will be estimated based on the stratified Cox regression model using Efron's method accounting for ties. Kaplan-Meier curves will be presented by treatment group. The number of participants, number of events, and number of censoring will be summarized by treatment group. The Kaplan-Meier estimate of median time will be presented with the 95% CI, which will be calculated using the method by Brookmeyer and Crowley (1982).

7.6. Analysis of Exploratory Efficacy Parameters

8.2. Pharmacodynamic

Expression of select biomarkers in the skin and peripheral blood at baseline and Week 12 will be summarized by descriptive statistics by treatment group. The purpose of these analyses will be to retrospectively evaluate biomarkers related to treatment and/or the biology of disease alone and in the context of treatment.

9. SAFETY AND TOLERABILITY

Appendix A provides a list of data displays. Sample data displays are included in a separate document.

9.1. General Considerations

The analyses in this section will be provided for the Safety Population in the DBVC period, the OLE Safety Population in the OLE period, and those who applied ruxolitinib 1.5% cream throughout the study, unless otherwise specified. Summary tables may be replaced with listings when appropriate. For instance, an AE frequency table may be replaced with a listing if it only contains a few unique preferred terms reported on relatively few participants.

9.2. Adverse Events

9.2.1. Adverse Event Definitions

A TEAE is any AE either reported for the first time or worsening of a pre-existing event after first application of study drug and within 30 days of the last application of study drug. For participants who cross over treatments, the first application date is period-specific; the end date is 30 days after the last application date in this period, or the first application date in the next period, whichever comes first. Analysis of AEs (as discussed below) will be limited to TEAEs, but data listings will include all AEs regardless of their timing in relation to study cream application.

Adverse events will be tabulated by MedDRA PT and SOC. Severity of AEs will be graded using the NCI CTCAE v5.0. The CTCAE reporting guidelines and grading details are available on the Cancer Therapy Evaluation Program website.

The subset of AEs considered by the investigator to be related to study cream will be considered to be treatment-related AEs. If the investigator does not specify the relationship of the AE to study cream, the AE will be considered to be treatment-related. The incidence of AEs and treatment--related AEs will be tabulated. In addition, serious TEAEs will also be tabulated.

Any missing onset date, causality, or severity must be queried for resolution. Unresolved missing causality and severity will be handled according to the following rules:

- An unresolved missing causality will be considered treatment-related.
- An unresolved missing severity will be identified as an unknown severity.

For purposes of analysis, all AEs will be considered TEAEs unless the AE can unequivocally be defined as not treatment-emergent.

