6. STUDY TREATMENT

6.1. Study Treatments Administered

Ruxolitinib 1.5% cream or matching vehicle cream will be applied as a thin film BID on each pruriginous lesion and the surrounding area of the lesion (~ 1 cm), with applications at least 8 hours apart in the morning and in the evening at least 1 hour before bedtime.

On Day 1 and at Week 12 (if applicable), the participant will apply a thin film of study cream to the treatment area under the supervision of site staff. The treatment area is defined as the area affected by pruriginous lesions plus an \sim 1 cm area surrounding each lesion. During the DBVC period, all other applications of study cream will be applied by the participant to the treatment area identified at baseline. The total BSA treatment area must be \leq 20%. Participants should not apply the application of study cream at home prior to clinic visits at Week 2, Week 12/EOT1, and Week 52/EOT2 (see Section 8.5).

At the baseline visit, an estimate of the %BSA treatment area will be used by the IRT system to calculate the number of tubes of study cream to be dispensed. All areas identified at baseline should continue to be treated through the end of the DBVC period (Week 12) unless the participant meets criteria for stopping study cream (see Section 6.5.2). If there are new pruriginous lesions to be treated, after consultation with the investigator, study cream should be applied to these lesions in addition to the areas treated at baseline (total BSA treatment area must be $\leq 20\%$), and the percentage of BSA to be treated will be recalculated and increased. This new estimate will be entered into the IRT system to calculate the number of tubes of study cream to be dispensed.

During the OLE period starting at the Week 12 visit, pruriginous lesions will be evaluated by the investigator to confirm whether the participant still requires continuation of therapy (ie, IGA-CPG-S score ≥ 1 and/or the presence of itching related to PN). Participants with an IGA-CPG-S score of 0 may continue or restart therapy if there is itch associated with underlying PN, or they can otherwise (re)enter the observation/no-treatment cycle (ie, IGA score of 0 and WI-NRS score of 0). At Week 12, the IRT system will dispense a prespecified number of tubes according to the assessment of total BSA treatment area.

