10.4.4. Safety Analyses

Safety analyses will be conducted for the safety population. A TEAE is any AE either reported for the first time or worsening of a pre-existing event after first application of study cream. Analysis of AEs will be limited to TEAEs, but data listings will include all AEs regardless of their timing to study cream application. Adverse events will be tabulated by the MedDRA preferred term and system organ class. Severity of AEs will be based on the National Cancer Institute CTCAE v5.0 using Grades 1 through 5.

The subset of AEs considered by the investigator to have a relationship to study cream will be considered treatment-related AEs. If the investigator does not specify the relationship of the AE to study cream, then the AE will be considered treatment-related. The incidence of AEs and treatment-related AEs will be tabulated.

The clinical laboratory data will be analyzed using summary statistics; no formal treatment group comparisons are planned. Laboratory test values outside the normal range will be assessed for severity based on the normal ranges for the clinical reference laboratory. The incidence of abnormal laboratory values and shift tables relative to baseline will be tabulated.

Descriptive statistics and mean change from baseline will be determined for vital signs (blood pressure, pulse, respiratory rate, and body temperature) at each assessment time.

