11.1. Changes to Protocol-Defined Analyses

Coding has been corrected for the FACIT-Fatigue scale. Each item uses a 5-point scale ranging from "0 = not at all" to "4 = very much."

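### The SAP's 30-day TEAE cutoff, which the protocol definition lacks, makes tabulation of open-label events more than 30 days off cream depend on a later restart

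*SAP*

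**What the plan says.** Protocol 10.4.4 defines the term with a start and no end: "A TEAE is any AE either reported for the first time or worsening of a pre-existing event after first application of study cream".

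SAP 9.2.1 keeps the start and adds an end, so that an event must fall "after first application of study drug and within 30 days of the last application of study drug". For participants who cross over treatments the window is set by period: "the end date is 30 days after the last application date in this period, or the first application date in the next period", whichever is earlier. The same section states that "Analysis of AEs (as discussed below) will be limited to TEAEs", while "data listings will include all AEs regardless of their timing in relation to study cream application". Events of interest (SAP 9.2.2) are also restricted to treatment-emergent ones.

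SAP 11.1, the section for departures from the protocol's analyses, has one entry: "Coding has been corrected for the FACIT-Fatigue scale". The TEAE window is not mentioned.

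OLE dosing is intermittent. Protocol 6.1 says of participants without lesions or PN itch that "they can otherwise (re)enter the observation/no-treatment cycle (ie, IGA score of 0 and WI-NRS score of 0", and it allows a restart if lesions or itch return. Protocol 6.5 treats such a spell as a temporary interruption. Protocol Table 4 schedules an adverse event assessment at every OLE visit, and Protocol 8.9.1 foresees participants who have been off cream for at least 30 days when they reach Week 52.

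**The concern.** A 30-day tail after the last dose suits continuous treatment, where the last dose marks the end of exposure. In this OLE a participant may stop cream, stay in the study and start again, so which application was the last is known only in retrospect. Take two participants who stop on the same day and have the same event on the same later date, more than 30 days off cream. They are classified differently if one relapses afterwards and restarts. A safety classification should not depend on something that happens after the event.

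What is at stake is the OLE (.2) and entire-study (.3) adverse event tables, including the events of interest such as malignancies and cardiovascular or thromboembolic events. Participants in lasting remission remain in the denominators, but their later events cannot enter the numerators. Protocol 2.2.1 gives assessment of the safety of intermittent dosing as a reason for the 40-week OLE, and time off cream is part of that regimen.

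**Working it through.** The plan gives no figure to reproduce on this point. The check applies the two definitions to the same timelines.

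**Inputs**
- Protocol rule (10.4.4): onset after first application, no upper limit.
- SAP rule (9.2.1): the same, and onset no later than L + 30 days, where L is the last application. For anyone who applied cream in the OLE, which is the last treatment period, the general rule and the period-specific rule give the same L.
- OLE length: Week 12 to Week 52, 40 × 7 = 280 days (Protocol 4.1).
- Assumptions for illustration: Week w is Day 7w, so Week 52 is Day 364; cream is stopped on Day 150. A participant who restarts does so after the event and last applies cream on Day 364.

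**Step 1: classification.** Without a restart the SAP window closes on Day 150 + 30 = Day 180.

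| Onset day | Days off cream | Protocol | SAP, never restarts | SAP, restarts after the event |
|---|---|---|---|---|
| 160 | 10 | TEAE | TEAE | TEAE |
| 180 | 30 | TEAE | TEAE | TEAE |
| 181 | 31 | TEAE | not TEAE | TEAE |
| 200 | 50 | TEAE | not TEAE | TEAE |
| 240 | 90 | TEAE | not TEAE | TEAE |
| 300 | 150 | TEAE | not TEAE | TEAE |

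The two SAP columns part company from day 31 off cream. A restart that ends well before the event does not rescue it: with a last application on Day 260 the window closes on Day 290, and an onset on Day 300 is still excluded.

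**Step 2: follow-up outside the window.** For a final application at Week w, the days up to Week 52 that the SAP excludes are max(0, 364 − (7w + 30)).

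| Final application | Calculation | Days excluded | Share of 280 days |
|---|---|---|---|
| Week 12 | 364 − 114 | 250 | 89% |
| Week 24 | 364 − 198 | 166 | 59% |
| Week 36 | 364 − 282 | 82 | 29% |
| Week 44 | 364 − 338 | 26 | 9% |
| Week 48 | 364 − 366 | 0 | 0% |

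**Step 3: direction.** Every event that meets the SAP rule also meets the protocol rule, so the SAP numerator is equal or smaller. The OLE denominator is everyone who applied cream at least once in the OLE (SAP 5.3.3.1) and does not change. The percentages in SAP 9.2.3 can therefore only be equal or lower.

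The number of events lost cannot be computed. The documents give neither the share of participants in lasting remission nor their event rate.

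**The case against.** The strongest reply is that 30 days is the protocol's own figure. Protocol 8.9.1 limits reporting of new events in the safety follow-up period to 30 days after the last application, and Protocol 9.4 lifts the duty to seek serious events actively beyond that point. The SAP may only be making that limit operational, and a fixed post-treatment window is a legitimate choice. This explains the number but does not remove the dependence on a later restart. The limit in 8.9.1 concerns the time after the Week 52 or early termination visit, Protocol 8.4.1 requires monitoring for at least 30 days, and Table 4 keeps assessing events throughout the OLE. The reporting limits do leave some doubt about how completely events are captured in long spells off cream.

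A reader might infer that late events vanish from the report. They do not: Appendix A of the SAP plans listings of all adverse events, serious events (2.7.3) and events of interest (2.7.8), and SAP 9.2.3 allows a table with 2 or fewer participants to become a listing. But listings give no incidence. The default that "all AEs will be considered TEAEs unless the AE can unequivocally be defined as not treatment-emergent", and the SAP 4.1.4 rule for a missing last application date, keep in events with unclear timing. With applications recorded daily in the eDiary, an event dated 90 days off cream would not normally be unclear.

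The group affected may also be small. Entering a no-treatment cycle requires a score of 0 on both IGA-CPG-S and WI-NRS. The planning assumption for the looser Week 12 target, IGA-CPG-S 0 or 1 with at least a 2-grade improvement, is 40% on active cream (Protocol Table 12). This stands, and it limits the weight of the point.

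**Conclusion.** The point holds for OLE events more than 30 days after cream was stopped. The SAP adds an end to the protocol's definition without declaring it. In an intermittent regimen that end makes inclusion in the tables depend on whether the participant restarts after the event. The effect on OLE and entire-study incidences is in one direction, equal or lower, and its size is unknown.

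Three stronger readings are not supported:
- That every off-cream event needs a later restart to be counted. Events in the first 30 days off cream are tabulated either way.
- That 59% or 29% of events are lost. Those are shares of OLE follow-up time for hypothetical participants whose final application falls at Week 24 or Week 36.
- That the randomised safety comparison is distorted. Cream is applied continuously to Week 12 in the vehicle-controlled period. In the OLE all participants are assigned active cream, and the entire-study summary has a single ruxolitinib group (SAP 5.2).

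Nor does the absence of a data monitoring committee add to the point. The TEAE flag governs the report tables, and serious events go to the sponsor within 24 hours whatever their TEAE status (Protocol 9.4).

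The conclusion rests on a literal reading of the last application in SAP 9.2.1 and on events being recorded at the scheduled OLE visits. It merits correction before the OLE tables are produced and does not bear on the primary analysis.

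**What to change.** In SAP 9.2.1, for the OLE (.2) and entire-study (.3) adverse event tables, tabulate all new or worsened events from first application in the period to the end of study participation, in line with Protocol 10.4.4. Flag each event as on-cream if onset is within 30 days of the most recent application before onset, and off-cream otherwise. Apply the flag to every cycle regardless of any later restart. If the 30-day TEAE table is kept, present it alongside and declare the departure in SAP 11.1.

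The cost is SAP wording and one derived flag, from event and application dates that the study already collects. The downside is that some background events off drug enter the tables, so incidences may be slightly higher; the flag lets a reader separate them.

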9.2.2. Adverse Events of Interest

Treatment-emergent AEs of interest will be summarized in the following categories:

- Cytopenias
 - Anemia
 - Thrombocytopenia
 - Neutropenia
- Herpes zoster
- Viral skin infections
- Serious infections
- Liver function test elevations
- Malignancies, excluding nonmelanoma skin neoplasms
- Nonmelanoma skin neoplasms
- Major adverse cardiovascular events
- Venous and arterial thromboembolic events
- ASRs

9.2.3. Adverse Event Summaries

An overall summary of AEs by treatment group will include the following:

- Number (%) of participants reporting any TEAEs
- Number (%) of participants reporting any serious TEAEs
- Number (%) of participants reporting any Grade 3 or higher TEAEs
- Number (%) of participants reporting any treatment-related TEAEs
- Number (%) of participants who temporarily interrupted study treatment because of TEAEs
- Number (%) of participants who permanently discontinued study treatment because of TEAEs

- Number (%) of participants who had any fatal TEAEs
- Number (%) of participants reporting any ASRs

The following summaries will be produced by MedDRA term. If 2 or fewer participants appear in a table, a listing may be provided instead of a summary table.

- Summary of TEAEs by MedDRA SOC and PT
- Summary of TEAEs by MedDRA PT in decreasing order of frequency
- Summary of TEAEs by MedDRA SOC, PT, and maximum severity
- Summary of TEAEs by MedDRA SOC, PT, and CTCAE grade category
- Summary of Grade 3 or higher TEAEs by MedDRA SOC and PT
- Summary of Grade 3 or higher TEAEs by MedDRA PT in decreasing order of frequency
- Summary of serious TEAEs by MedDRA SOC and PT
- Summary of serious TEAEs by MedDRA PT in decreasing order of frequency
- Summary of treatment-related TEAEs by MedDRA SOC and PT
- Summary of treatment-related TEAEs by MedDRA PT in decreasing order of frequency
- Summary of Grade 3 or higher treatment-related TEAEs by MedDRA SOC and PT
- Summary of treatment-related serious TEAEs by MedDRA SOC and PT
- Summary of TEAEs leading to application interruption by MedDRA SOC and PT
- Summary of TEAEs leading to discontinuation of study cream by MedDRA SOC and PT
- Summary of ASRs by MedDRA PT in decreasing order of frequency
- Summary of TEAEs of interest

9.3. Clinical Laboratory Tests

The analyses in this section will be provided for the Safety Population in the DBVC period and the OLE Safety Population in the OLE period unless otherwise specified.

9.3.1. Laboratory Value Definitions

All laboratory assessments will be performed using a central laboratory, with the exception of urine pregnancy tests (as applicable). Laboratory values and change from baseline values will be summarized descriptively by visit. Baseline will be determined according to Section 4.1.3, using the last nonmissing value collected before the first application, prioritizing scheduled assessments for baseline identification over unscheduled visits. The last record before application in the highest priority will be considered the baseline record. If there are multiple values that meet the criteria for baseline, additional rules may be provided after consultation with the medical monitor to delineate which value will be defined as baseline.

9.3.2. Laboratory Value Summaries

All test results and associated normal ranges from central laboratories will be reported in SI units. All tests with numeric values will have a unique unit per test. Any laboratory test results and associated normal ranges from local laboratories will be converted to SI units.

When there are multiple nonmissing laboratory values for a participant's particular test at a scheduled visit, central laboratory values have higher priority over local laboratory values. If a tie still exists, the laboratory value with the smallest laboratory sequence number will be used in by-visit summaries.

Numeric laboratory values will be summarized descriptively in SI units, and non-numeric test values will be tabulated when necessary. In addition, box-and-whisker plots will be provided for select laboratory values.

For test results that will be summarized with available normal ranges, the number and percentage of participants with the laboratory values being low (but never high), normal, high (but never low), and both low and high will be calculated for each test. A shift summary will be produced for each test. The denominator for the percentage calculation will use the number of participants in the baseline category (ie, low, high, normal, or missing) as the denominator for the percentage in each of the categories during the study.

Severity grades will be assigned to laboratory test values based on the numerical component of CTCAE v5.0. Shift tables will also be presented showing change in CTCAE grade from baseline to the worst grade postbaseline. Separate summaries for abnormally high and abnormally low laboratory values will be provided when the laboratory parameter has both high and low grading criteria. The denominator for the percentage calculation will be the number of participants in the baseline category. The number of participants who had worsening of laboratory abnormalities will be summarized by maximum severity.

9.4. Vital Signs

The analyses in this section will be provided for the Safety Population in the DBVC period and the OLE Safety Population in the OLE period unless otherwise specified. Values at each scheduled visit, change, and percentage change from baseline for vital signs, including systolic blood pressure, diastolic blood pressure, pulse, temperature, and respiratory rate will be summarized descriptively.

Normal ranges for vital sign values are defined in Table 6. For participants exhibiting vital sign abnormalities, the abnormal values will be listed along with their assigned treatment group. Alert vital signs are defined as an absolute value outside the defined normal range and percentage change greater than 25%. The abnormal values for participants exhibiting alert vital sign abnormalities will be listed.

Table 6: Criteria for Clinically Notable Vital Sign Abnormalities

Parameter	High Threshold	Low Threshold
Systolic blood pressure	> 155 mmHg	< 85 mmHg
Diastolic blood pressure	> 100 mmHg	< 40 mmHg
Pulse	> 100 bpm	< 45 bpm
Temperature	> 38°C	< 35.5°C
Respiratory rate	> 20 breaths/min	< 8 breaths/min

10. PLANNED ANALYSES

No formal interim analysis is planned in this study.

There are 2 formal planned analyses as follows:

- The primary analysis will occur after the primary database lock, when all participants have completed or discontinued from the DBVC period. The sponsor will be unblinded after the primary database lock; however, investigators and participants will remain blinded to the individual study treatment assignment after the primary database lock.
- The final analysis will occur when all participants have completed or withdrawn from the study.

If the p-value for the primary endpoint is deemed insignificant in the primary analysis outlined in Section 7.3.1, the study will be terminated due to a lack of demonstrable efficacy benefits for the participants.

11. CHANGES AND MODIFICATIONS TO THE ANALYSIS PLAN

All versions of the SAP are listed in Table 7.

Table 7: Statistical Analysis Plan Versions

SAP Version	Date
Original	15 JUL 2024

11.1. Changes to Protocol-Defined Analyses

Coding has been corrected for the FACIT-Fatigue scale. Each item uses a 5-point scale ranging from "0 = not at all" to "4 = very much."

